4.2 Prior and Concomitant Therapy

Details of relevant current and concomitant medications administered during the trial period will be recorded on the CRF. Relevant medications are defined as follows:

- Plasma products (e.g., octaplas™, regular plasma products, etc.) and all other blood products that are administered.
- Antifibrinolytics (ε-aminocaproic acid or tranexamic acid) and any other pharmaceutical pro- or anti-coagulants such as recombinant activated factor VII, any of the prothrombin complex concentrates, or fibrinogen concentrates.
- Vaso-active agents (epinephrine, norepinephrine, vasopressin, Milrinone, phenylephrine, Antidiuretics (desmopressin, DDAVP, DesmoMelt, Stimate, Minirin, etc.).
- Colloids (e.g., albumin, hydroxyethyl starches).
- Medications (including steroids) taken to treat or prevent ADRs (to Octaplas)
- Other medications that the Investigator considers relevant to report for this trial.

Routine medications that are considered standard and/or that have little or no impact on the study data results are not to be entered into the CRF (e.g., anesthesia medications, beta blockers, etc.). Any concomitant medications or changes thereof must be recorded. If the change influences the patients' eligibility to continue in the trial, the Sponsor must be informed.

Permitted Concomitant Therapy

The following concomitant medications are permitted:

- calcium-gluconate given IV in case of hypocalcemia (due to citrate toxicity),
- antihistamines and glucocorticoids given IV in case of anaphylactoid reactions, and
- red blood cells, platelet units if medically indicated.

It is permitted for patients to receive Octaplas or other plasma products (please see exceptions below) during the 72-hour follow-up period if medically indicated.

Although patient's requiring ECMO at study entry are excluded, ECMO is permitted therapy while on study if it is determined to be medically indicated after the start of the first infusion.

Forbidden Concomitant Therapy

Single donor plasma (e.g., FFP, FP24, thawed plasma, etc.) should be avoided during the Treatment and Follow-up study periods. Patients receiving single donor plasma during the Treatment or Follow-up periods should be withdrawn from the trial.

Plasma exchange, TPE or plasmapheresis is not permitted during the study. Patients who develop the need for and undergo plasma exchange or plasmapheresis during the Treatment or Follow-up periods will be withdrawn from the trial.

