Hemostatic parameters will be presented descriptively per time point, including shift tables. Individual courses of hemostatic parameters will be presented graphically as Trellis plots.

Vital sign measurements will be summarized by descriptive statistics, including shift tables. All measurements outside age-specific thresholds will be listed and reviewed individually.

All safety laboratory data – absolute values as well as changes from baseline – will be presented descriptively per time point. All measurements outside age-specific thresholds will be listed and reviewed individually.

All data will be presented in total as well as in sub-groups reflecting age (\leq and $>$ 2 years respectively), gender, underlying diagnosis, surgical procedures performed and/or most relevant medical history and concomitant medications.

Population for Analysis

The Safety (SAF) population will include all patients who received at least one infusion of Octaplas.

The full analysis set (FAS) is defined according to the intent-to-treat (ITT) principle and will include all patients of the SAF with any measurements on the primary endpoint variables (monitored for ADRs, hemostatic parameters, safety laboratory parameters, vital signs, etc.).

Patients who are consented (enrolled) to participate prior to an operative procedure and then did not get transfused will not be included in the ITT analysis.

The per-protocol (PP) population will include all patients who have completed the infusion episode(s) and the final examination without major protocol deviations, which may have an impact on the evaluation of the primary study outcome parameter(s). Examples of protocol deviations to be considered in this respect would be dosing errors, the use of prohibited concomitant medications, or the occurrence of completely unrelated medical events that

require an interruption of the study procedures. The final decision regarding inclusion/exclusion of patients from the analysis sets will be taken by a panel including the CPM, the study statistician and a medical expert during a data review meeting before database lock. The decisions taken will be based on a review of complete data listings, and documented before the database is locked and the analysis is performed.

Efficacy Analysis Plan

The analysis of the efficacy parameters will be performed for the ITT and PP populations.

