5.2. Final Analyses and Reporting

Due to the complex and highly variable and individual medical circumstances and interventions that are to be expected in this study, no single parameter or measurement of outcome is chosen as the primary endpoint. All data collected will be summarized and presented descriptively to facilitate the review of population homogeneity and general patterns within and between patients of similar baseline characteristics or disease patterns. No confirmatory hypothesis testing is planned. Any p-value or confidence interval presented is to be understood in the exploratory sense.

To allow a holistic review and interpretation of each course of treatment, all parameters relevant for the assessment of safety will be presented descriptively in full detail, by subgroups of interest as well as in total. The safety assessment will include the occurrence of SAEs, ADRs, TEs, TEEs and hyperfibrinolytic events. To facilitate the detection of any possible safety signal, all these events will be characterized and analyzed by age (\leq and $>$ 2 years of age respectively), underlying diagnosis, seriousness, severity, relation to study drug and timely relationship to study drug administration. In addition to these pre-planned categories, the collected data will be examined to identify additional characteristics of interest such as particular types of surgeries or procedures, relevant concomitant medications, or Standardized MedDRA Queries (SMQs) covering a noticeable number of events. The occurrences of all specific safety events will be presented for all these categories and in total, together with the associated 95% confidence intervals.

The following subgroups/categories were identified during the ongoing medical review, and will be considered in the presentation of safety data as detailed above:

- Underlying Diagnosis
 - Congenital heart disease
 - Liver disease requiring transplant
 - Sepsis related coagulopathy
- Types of surgery
 - Cardiac
 - Orthotopic liver transplant
 - None
- No further characteristics were identified in medical history, concomitant medications or reported AE terms that called for further subgroup analyses.

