To account for the abovementioned diversity in the study population, individual patient profiles will be generated, displaying the baseline characteristics as well as all interventions, treatment details and relevant measurements on a time scale. This will facilitate the review of each individual course of treatment by the trial medical monitor or expert to assess the efficacy of the treatment but also to detect any safety signal that might not be reflected in the ADR rates.

Hemostatic parameters will be presented descriptively per time point, including shift tables. Individual courses of hemostatic parameters will be presented graphically as Trellis plots.

Vital sign measurements will be summarized by descriptive statistics, including shift tables. All measurements outside the age-specific thresholds defined in the trial validation plan and/or the TFLs document will be listed and reviewed individually.

All safety laboratory data – absolute values as well as changes from baseline – will be presented descriptively per time point. All measurements outside the age-specific thresholds defined in the trial validation plan and/or the TFLs document will be listed and reviewed individually.

All data will be presented in total as well as in sub-groups reflecting age (\leq and $>$ 2 years), gender, underlying diagnosis, surgical procedures performed as detailed above and to the extent appropriate.

6. Sample Size Determination

The chosen number of 50 pediatric patients is not derived from statistical considerations of power, but to gather enough clinical evidence to obtain a sound and meaningful medical assessment and sufficient safety information in a reasonable amount of time.

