8.3. Handling of Missing Data

In general, missing data will not be imputed.

No analyses of the patterns of missing data will be done.

For medications the following will be applied: A medication will be assumed to be concomitant if it can be definitely shown that the medication was administered after start of the first Octaplas infusion and before the end of the observation period. Missing dates will not be replaced.

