9.4. Measurement of Treatment Compliance

The following parameters will be listed and/or summarized per patient and/or per infusion:

- Body weight
- Actual dose (total and per kg body weight, based on the latest available weight measurement)

- Total dose of Octaplas administered
- Total number of infusions administered
- Total number of bags and total volume of solution administered
- Infusion times and rates (mL/kg/min)
- Overall amount of product administered and batches used (only included in data listings)

During ongoing medical review it was noted that particular infusion patterns associated with cardiac surgeries due to the use of bypass circulation devices in clinical practice were not foreseen beforehand. To account for this the following categorization will be introduced for the analysis of infusion speed and dosing:

- Normal infusion
- Bypass priming
- Bypass warming up

10. Efficacy Analysis

This study will examine the efficacy of Octaplas by measuring hemostatic parameter improvements reflecting changes in hemostasis.

The following hemostatic parameters will be assessed: INR, PT, aPTT and TEG with Kaolin activation or ROTEM EXTEM. Pre- and post-infusion episode samples for hemostatic and laboratory parameters will be tested. The pre-infusion episode laboratory samples should be drawn within 6 hours before the start of the first infusion episode and within 60 minutes prior to the start of the subsequent infusion episodes. Post-infusion episode samples should be drawn within 30 to 60 minutes after the end of each infusion episode.

Beside the complete descriptive and graphical presentations of all available parameters as described above (see sections 5.2 and 8), the actual data collected might suggest additional factors that potentially affect the hemostatic parameters after the results from the planned analysis are completed; in this case full details of additional analyses with respect to such covariates will be given in the CSR.

All efficacy endpoints will be presented on basis of both, the FAS and the PP analysis sets, to allow for an assessment of the robustness of the results with respect to protocol violations. The FAS analysis is considered to be the primary assessment of efficacy, and will be presented first in the report.

11. Safety and Tolerability Analyses

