The primary objective of LAS-212 is to assess the safety and tolerability of Octaplas in the pediatric population by monitoring serious adverse events (SAEs), adverse drug reactions (ADRs), thrombotic events (TEs), thromboembolic events (TEEs) and hyperfibrinolytic events, including laboratory parameters for metabolic derangements, renal function, and hematologic implications.

This will be done by means of descriptive analyses of all safety related data available.

The analysis of the safety parameters will be performed for the SAF population.

The occurrence of SAEs, ADRs, TEs, TEEs and significant hyperfibrinolytic events will be reported. All these events will be characterized and analyzed by underlying diagnosis, seriousness, severity, relation to study drug and timely relationship to study drug administration. Subgroup analyses will be conducted for hyperfibrinolytic events in patients who undergo liver transplant.

All safety laboratory data – absolute values as well as changes from baseline – will be presented descriptively per time point. All measurements outside age-specific thresholds will be listed and reviewed individually.

All data will be presented in total as well as in sub-groups reflecting age (\leq and $>$ 2 years), gender, underlying diagnosis, and surgical procedures performed as detailed in section 5.2.

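### The SAP plans no display of lysis, thrombotic events or clotting changes by antifibrinolytic or procoagulant use, and its timing rule undercounts concomitant medicines

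*SAP*

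**What the plan says.** **Subgroups.** The sentence in Protocol 9.2 that lists subgroups for all data ends with "surgical procedures performed and/or most relevant medical history and concomitant medications"; the synopsis has the same ending. The matching sentence in SAP 5.2 ends with "gender, underlying diagnosis, surgical procedures performed as detailed above and to the extent appropriate", and the one in SAP 11 with "gender, underlying diagnosis, and surgical procedures performed as detailed in section 5.2". Neither mentions concomitant medications.

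**Stated reason.** SAP 5.2 still names, among things the data will be examined for, "relevant concomitant medications, or Standardized MedDRA Queries (SMQs) covering a noticeable number of events". It then lists the diagnosis and surgery categories found during ongoing medical review and closes with "No further characteristics were identified in medical history, concomitant medications or reported AE terms that called for further subgroup analyses".

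**What is recorded.** Protocol 4.2 defines as relevant all blood products, antifibrinolytics and "any other pharmaceutical pro- or anti-coagulants such as recombinant activated factor VII", along with prothrombin complex and fibrinogen concentrates. The flow-chart notes in Protocol 3.2 require other transfusion products to be captured individually.

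**Timing rule.** SAP 8.3 sets one test for every drug: it "will be assumed to be concomitant if it can be definitely shown that the medication was administered after start of the first Octaplas infusion". Use must also fall within the observation period. Missing dates are not replaced.

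**Covariates.** Protocol 9.2 leaves covariate adjustment to the SAP. SAP 10 names no covariate and says only that "the actual data collected might suggest additional factors that potentially affect the hemostatic parameters after the results from the planned analysis are completed", in which case details go in the study report.

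**The concern.** The recorded co-treatments act on the trial's own endpoints. Protocol 7.3.4 defines a hyperfibrinolytic event by lysis above 7.5% at 30 minutes on TEG or ROTEM, together with a bleed that needs intervention; an antifibrinolytic lowers that lysis. Procoagulant concentrates can raise thrombotic risk. Cryoprecipitate, platelets and concentrates given between the pre- and post-infusion samples can move INR, PT, aPTT and TEG/ROTEM.

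Hyperfibrinolysis and thrombosis are risks that the protocol and package insert name for this product. In a single-arm study, a low lysis incidence might partly reflect antifibrinolytic use, a thrombotic event might follow a concentrate, and a better clotting test might follow cryoprecipitate. As planned, a reader of the pooled incidences and mean changes could not see whether this happened. The 8.3 rule adds to the problem: any later attempt to split by exposure would start from an exposure flag that errs towards not exposed.

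**Working it through.** **1. No planned figure to reproduce.** The SAP states that the 50 patients do not come from a power calculation, and the documents give no event or exposure rates. The main check is textual; the numbers below are illustrations under stated assumptions.

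**2. Subgroup sentences side by side.**
- Protocol 9.2: age, gender, diagnosis, surgery and/or most relevant medical history and concomitant medications.
- SAP 5.2 and 11: age, gender, diagnosis, surgery.

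The last item is absent from both SAP sentences. SAP 9.3 tabulates prior and concomitant medications by ATC level but does not cross them with any outcome. The liver-transplant subgroup for hyperfibrinolytic events does not separate antifibrinolytic use.

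**3. The pre/post pair.** Protocol 3.2 allows the first pre-sample up to 6 hours before the episode. For plasma-primed bypass the episode runs from circuit initiation to heparin reversal, and the post-sample follows 30 to 60 minutes later. Such a pair spans the whole bypass period. SAP 9.4 adds bypass categories, but only for infusion speed and dosing, not for hemostatic change.

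**4. Effect of the 8.3 rule.** SAP 8.3 says when a medicine is concomitant and gives no separate rule for uncertain timing. On the ordinary reading, uncertain means not concomitant. Let f be the share of children truly exposed and m the share of those whose timing cannot be proven. The share of the apparently unexposed who were really exposed is f·m / (1 − f + f·m).

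| f | m | Calculation | Result |
|---|---|---|---|
| 0.5 | 0.1 | 0.05/0.55 | 9% |
| 0.5 | 0.3 | 0.15/0.65 | 23% |
| 0.8 | 0.1 | 0.08/0.28 | 29% |
| 0.8 | 0.3 | 0.24/0.44 | 55% |

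In heads, the last row is 40 of 50 exposed, 12 of them undated, so 12 of the 22 apparently unexposed were exposed.

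**5. Dilution in a pooled rate.** Let p0 be the lysis rate without an antifibrinolytic and RR the risk ratio with it. The pooled rate is p0·(1 − f + f·RR). Assume RR from 0.3 to 0.5 and f from 0.3 to 0.8.
- p0 = 10%: from 0.10 × (0.2 + 0.24) = 4.4% to 0.10 × (0.7 + 0.15) = 8.5%.
- p0 = 20%: from 0.20 × 0.44 = 8.8% to 0.20 × 0.85 = 17.0%.

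**6. Precision.** With 0 events in n children the exact two-sided 95% upper limit is 1 − 0.025^(1/n).
- All 50: 7.1%.
- Split 40 exposed and 10 not (assumption): 8.8% and 30.8%.
- Split 25 and 25 (assumption): 13.7% each.

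These limits illustrate imprecision under an assumed split. They are not evidence of bias.

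**7. What a split can show.** Over the assumptions in step 5, a two-sided 5% comparison of exposed and unexposed among 50 children (normal approximation) has power of 5.9% to 33.5%. A display makes confounding visible; it cannot resolve it.

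**The case against.** **Departure from the protocol.** A reader might infer that the SAP removed a planned analysis. The documents do not establish that. The protocol item is conditional, Protocol 9.2 itself foresees an examination of the data for further characteristics, and SAP 5.2 reports the outcome of such a review. The SAP also cites protocol Version 10 (29-Nov-2017), while the supplied protocol is dated 19-Nov-2016 and has different age caps (33/17 against 37/13 in the SAP). What stands is that the review's criterion is not documented and that it was done with open-label event terms in view.

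**Attribution to Octaplas.** A reader might infer that co-treatment effects will be reported as product effects, or that medication splits are the only safeguard. Neither is supported. The plan is descriptive. It counts SAEs, TEs, TEEs and hyperfibrinolytic events regardless of causality, grades causality with other drugs as a possible explanation, adjudicates TEs/TEEs, splits by diagnosis and surgery, and plots all interventions over time for expert review. These safeguards have limits. An event that an antifibrinolytic prevented is never graded, adjudication covers only TEs/TEEs, and profiles do not qualify a pooled incidence or mean change.

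**Hidden single donor plasma.** A reader might infer that 8.3 could conceal a forbidden unit. It does not govern the violation check: SAP 9.2 checks violations on complete data, and such plasma is barred both in the 72 hours before the first infusion (exclusion criterion 6) and during treatment and follow-up.

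**Reach of 8.3.** Prior medications are tabulated too, and nothing removes undated drugs from listings or profiles. That is correct and confines the harm to the exposure classification.

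**Value of the splits.** Co-treatment is driven by bleeding, so any split is confounded by indication, and cells will be small. Both points stand. The table list is a separate document that was not supplied, so displays could still be specified there.

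**Conclusion.** The point holds as a gap in prespecification. The SAP text contains no display of hyperfibrinolytic events, TEs/TEEs or hemostatic change by antifibrinolytic or procoagulant use. It gives an undocumented reason for having no medication subgroup, and it lets uncertain timing fall on the not-concomitant side. Without a control group, confounding by these recorded treatments may go unseen in the pooled results, with partial protection from the safeguards named above.

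Its size cannot be fixed from the documents. Under the assumed exposure and effect ranges, dilution of a pooled lysis rate is plausible, and the timing rule would put 9% to 55% truly exposed children among the apparently unexposed. Whether the SAP departs from its governing protocol remains unconfirmed without Version 10. The change is worth making because it is cheap, not because a bias has been shown.

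**What to change.** 1. **SAP 8.3.** Treat a medication or blood product as concomitant unless its record shows that it ended before the first Octaplas infusion or began after the observation period. Keep the strict rule as a sensitivity analysis.
2. **SAP 5.2 and 11.** Add descriptive displays of hyperfibrinolytic events by antifibrinolytic use before the event or test, and of TEs/TEEs by prior antifibrinolytic or procoagulant use. Define use by timing relative to the event, so that a drug given shortly before the first infusion is not lost under the prior label. State the criterion the medical review applied.
3. **SAP 10.** Flag each pre/post pair with cryoprecipitate, platelets, or a factor or fibrinogen concentrate given between the samples, and show the change for unflagged pairs beside all pairs. Show plasma-primed bypass pairs as a separate category. Do not flag for heparin reversal, because that would flag every such pair.

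**Cost.** SAP wording and a few tables from data already collected; the sample size does not change. The cells will be small, the displays remain confounded by indication, and some medicines given only before the first infusion will be labelled concomitant.

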6.1. Patient Replacement Policy

There is no patient replacement policy defined for this protocol.

6.2. Premature Termination of the Study

If early termination of the study becomes necessary for whatever reason, the sponsor and the investigator will ensure that adequate consideration is given to the protection of the patients' interests. Such a premature termination will be communicated in accordance with applicable regulatory requirements. The Investigator will promptly inform the Independent Ethics Committee (IEC)/Institutional Review Board (IRB) and provide a detailed written explanation. The pertinent regulatory authorities will be informed according to national regulations.

7. Analysis Populations

The following populations will be considered for the statistical analysis:

The safety population (SAF) will include all patients who received at least one infusion of Octaplas.

The full analysis set (FAS) is defined according to the intent-to-treat (ITT) principle and will include all patients of the SAF with any measurements on the primary endpoint variables (monitored for SAEs, ADRs, hemostatic parameters, safety laboratory parameters, vital signs, etc.).

The per-protocol (PP) population will include all patients who have completed the infusion episode(s) and the final examination without major protocol deviations, which may have an impact on the evaluation of the primary study outcome parameter(s).

All protocol violations documented during the conduct of the study or identified at the data review process prior to DB lock will be reviewed and classified as minor or major and with respect to its effect on the planned analysis. Only major protocol violations with the potential to significantly affect the study results or to invalidate the interpretation of the data obtained will lead to exclusion of patients from the PP set. This classification of protocol violations is the joint responsibility of the clinical study manager, the study statistician, and Octapharma's responsible medical expert, and will be performed and documented before the database is locked and the statistical analyses are performed.

Examples of protocol deviations to be considered in this respect would be violations of the study entry criteria, dosing errors, the use of forbidden concomitant medications, or the occurrence of completely unrelated medical events that require an interruption of the study procedures. The final decision regarding inclusion/exclusion of patients from the analysis sets will be taken by a panel including the Clinical Project Manager, the study statistician and a medical expert during a data review meeting before database lock. The decisions taken will be based on a review of complete data listings, and documented before the database is locked and the analysis is performed.

8. General Issues for Statistical Analysis

Descriptive summaries will be presented for each of the primary and secondary variables. In general, summaries will be completed for all patients overall and by groups of particular interest as indicated by the data. Continuous, quantitative variable summaries will include the number of patients with non-missing values (N), mean, standard deviation, median, minimum and maximum, 1st and 3rd quartile.

Categorical, qualitative variable summaries will include the frequency and percentage of patients who are in the particular category. In general the denominator for the percentage calculation will be the total number of patients in the analysis population unless otherwise specified.

